### **7.3 Duration of Participation**

Describe how long subjects will be involved in this research study. Include the number of sessions and the duration of each session - consider the total number of minutes, hours, days, months, years, etc.

Schools will be enrolled in the study for the 2021/2022 school year. The duration of the pre- and post-surveys is approximately 10-15 minutes. The duration of the semi-structured interviews will be approximately 15-20 minutes if being interviewed individually or 25-35 minutes in length if two individuals are being interviewed at the same time.

The school staff members who complete the “Educator Training Feedback Survey” is limited to the 5 minutes it takes for them to complete it.

## **8.0 Number of Subjects and Statistical Plan**

## 8.1 Number of Subjects

Indicate the maximum number of subjects to be accrued/enrolled. Distinguish between the number of subjects who are expected to be enrolled and screened, and the number of subjects needed to complete the research procedures if applicable (i.e., numbers of subjects excluding screen failures.)

A total of 10 high schools will be enrolled in the study, representing nearly 1,000 students.

### School Staff Semi-structured Interviews

Up to 50 (35 faculty/staff members from each of the 10 high schools).

## 8.2 Sample size determination

If applicable, provide a justification of the sample size outlined in section 8.1 to include reflections on, or calculations of, the power of the study.

### Student Pre- and Post- Survey

The sample size was chosen primarily based on feasibility of enrolling schools, implementing the Aevidum curriculum at all schools, and setting up school-specific processes for collecting data at each school. A total of 10 schools was deemed feasible.

When determining the number of schools to enroll, the study team took the following into consideration: 1) Retention and changes in school administration and their priorities, which impacted the ability of schools to participate as planned in the context of PRO Wellness's SHIELD study. 2) the number of schools which could implement Aevidum 3) Results of a previous school-based study conducted by Parikh et al. (2018) that used the UMDC survey instrument. The Parikh study included ten high schools and found a number of significant differences over time. We anticipate the same potential for this work that will include more schools and students. We have added two additional schools in this proposal and will plan to keep a "waitlist" of schools interested in participation, as schools will continue to utilize the curriculum and club independently of the proposed study. This will allow us to replace a school that ultimately decides not to participate.

### School Staff Semi-structured Interviews

N/A

## 8.3 Statistical methods

Describe the statistical methods (or non-statistical methods of analysis) that will be employed.

### Student Pre- and Post- Survey

In primary statistical analysis, schools implementing only the curriculum (Aim 1) and schools implementing the curriculum and club activities (Aim 2) will be analyzed separately, using the same methods. Descriptive statistics will be calculated and survey items will be presented graphically over time. Mixed effects linear and logistic regression models appropriate for longitudinal (repeated measures) data will be used to analyze all survey items collected at each time point. The models will contain a fixed effect for time (pre vs. post) and random effects for school and student. The parameter for time is the primary parameter of interest in the model, as it indicates the change over time with intervention implementation. Parameter estimates and standard errors from the models will be reported along with corresponding 95% confidence intervals and p-values.

In secondary statistical analysis, we will compare the curriculum-only schools to the curriculum plus club activities schools directly.

Specifically: 1) Compare students from schools in Aim 1 (curriculum only) to those in Aim 2 (curriculum plus club) regarding changes in knowledge, help-seeking behavior, school environment/stigma and program visibility.

2) Compare the impact on 9th graders in curriculum schools versus 9th graders in curriculum plus club schools.

The same mixed effects regression models will be used for each survey item, except that the model will also include fixed effects for group (curriculum-only vs. curriculum plus club activities) and a group by time interaction effect. A positive interaction effect indicates that schools which implemented curriculum and club activities had larger changes over time than curriculum alone.

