**7.1 Study Design**

Describe and explain the study design.

This study design is a cluster randomized trial. Schools will be randomized to implement either the Aevidum curriculum alone (n=5) or Aevidum curriculum plus club activities (n=5). Students in grades 9-12 at each school whose parents did not opt them out will be asked to complete pre- and post-surveys. School staff who participated in the Aevidum curriculum training will be asked to complete the “Educator Training Feedback Survey”.

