### Schools

The 5 of the 10 schools that are randomly assigned to implement 2 Aevidum club activities will receive a \$1,000 stipend to support club activities during the 21-22 academic school year. The remaining 5 schools who are randomly assigned to implement just the Aevidum curriculum will receive a \$1,000 stipend for club activities at the end of the 2021-2022 school year after completion of the research.

An incentive will be offered to schools who have post-survey completion rates of 60%. Schools who hit this goal will be sent an additional \$100 stipend to put towards their Aevidum club.

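### The mixed models have no school-by-time effect, so the tests of change treat students within a school as independent

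*Combined protocol and SAP*

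**What the plan says.** Section 7.1 makes the school the unit of allocation: "This study design is a cluster randomized trial", with five schools per arm. Section 8.1 gives the size: "A total of 10 high schools will be enrolled in the study, representing nearly 1,000 students".

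Section 8.3 analyses each arm separately in the primary analysis, using linear and logistic mixed models. Their terms are listed in full: "The models will contain a fixed effect for time (pre vs. post) and random effects for school and student". It adds that "The parameter for time is the primary parameter of interest in the model". The secondary analysis keeps the same models, except that "the model will also include fixed effects for group (curriculum-only vs. curriculum plus club activities) and a group by time interaction effect". On reporting: "Parameter estimates and standard errors from the models will be reported along with corresponding 95% confidence intervals and p-values".

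Neither model has a school-by-time random effect or a random time slope by school. Cluster-robust standard errors and a small-sample degrees-of-freedom method are not mentioned anywhere in the document.

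**The concern.** Both tests that matter concern change from pre to post. A school intercept and a student intercept are the same at both surveys, so they drop out of a change. The model therefore handles clustering of survey levels, which neither test uses, and omits clustering of change, which both tests need.

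The protocol gives reasons to expect change to differ between schools:

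- Section 1.1 lets each school split the lessons and fit them into its own health teaching at any time before February 2022. Club schools choose their own leaders.
- Section 7.2.2 puts the post-survey in April-May 2022, so the time since delivery varies by school.
- Section 7.2 gives the curriculum to ninth graders only, while grades 9-12 are surveyed. The grade mix of responders can therefore shift a school's average change.
- Section 4.1 deliberately seeks schools that differ in locale, socioeconomic status and demographics.

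If that variation exists, the standard errors of time and of group by time are too small. The reported 95% intervals and p-values then lack their stated coverage and error rate. With five schools per arm, a normal reference distribution would also be too narrow once school variation is counted.

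**Working it through.** The document states no power, intraclass correlation or variance, so there is no figure of its own to reproduce.

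**Inputs from the document**

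- Five schools per arm (Section 7.1).
- About 1,000 students in 10 schools (Section 8.1), so 1,000/10 = 100 per school on average.
- 60% post-survey completion is an incentive threshold in Section 13.0, not a forecast. It is used here only to set a lower case of 0.60 × 100 = 60 pairs per school.

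**Assumptions**

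- Two-sided 5% level.
- Total variance 1 and residual variance σ² = 0.5.
- A separate school effect at each survey occasion, with variance τ² = 0.005, 0.01 or 0.02 (0.5%, 1% or 2% of total).

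**Step 1: what cancels.** The planned model for student i in school j at time t is y = β₀ + β₁t + u_j + v_ij + e_ijt. The change is d_ij = β₁ + (e_ij2 − e_ij1), so u and v are gone. With J schools and m pairs per school, the model's variance for the time effect is 2σ²/(Jm).

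**Step 2: what should be there.** With school-by-occasion effects w_jt, the change also contains w_j2 − w_j1, and the true variance is

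(2τ² + 2σ²/m)/J = [2σ²/(Jm)] × (1 + mτ²/σ²).

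The inflation factor VIF = 1 + mτ²/σ² is the same for time within an arm and for group by time between arms.

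**Step 3: check by fitting.** Random-intercept models were fitted to simulated complete pairs:

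| Test | Planned-model SE | Independent-students SE | School-level SE |
|---|---|---|---|
| time | 0.0535 | 0.0535 | 0.085 |
| time | 0.0589 | 0.0589 | 0.0823 |
| group by time | 0.0854 | 0.0854 | 0.1239 |
| group by time | 0.0883 | 0.0883 | 0.2158 |
| group by time | 0.0912 | 0.0912 | 0.2015 |
| group by time | 0.0867 | 0.0867 | 0.1510 |

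The first two columns agree in every fit. The third depends on the variance that was simulated, so it shows the mechanism and not the size expected in this trial.

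**Step 4: type I error** = 2 × [1 − Φ(1.96/√VIF)].

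| τ² | m = 60: VIF | type I | m = 100: VIF | type I |
|---|---|---|---|---|
| 0 | 1.0 | 5.0% | 1.0 | 5.0% |
| 0.005 | 1.6 | 12.1% | 2.0 | 16.6% |
| 0.01 | 2.2 | 18.6% | 3.0 | 25.8% |
| 0.02 | 3.4 | 28.8% | 5.0 | 38.1% |

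Simulation with five schools per arm (6,000 replicates) agreed at m = 60: 11.8%, 18.7% and 28.1% for time; 12.4%, 18.6% and 28.8% for group by time.

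**Step 5: the same calculation on another scale.** Let ρ be the share of change-score variance that lies between schools, so that ρ = τ²/(τ² + σ²). Then τ² = 0.005 gives 0.005/0.505 ≈ 0.01, and τ² = 0.01 gives 0.01/0.51 ≈ 0.02. With design effect 1 + (m − 1)ρ, type I error at ρ = 0.01 and 0.02 is 12.0% and 18.4% for m = 60, and 16.5% and 25.6% for m = 100.

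**Step 6: the remedy.** In 4,000 replicates per setting, with ρ from 0 to 0.05, t tests on school-mean changes (4 df within arm, 8 df between arms) had type I error between 4.2% and 5.5%.

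**The case against.** **The wording.** Section 8.3 says random effects, not random intercepts, and calls the models suitable for longitudinal data. A school slope may have been meant. Intercepts are the ordinary reading, however, and no slope is named in either model. If one was intended, the same sentence is still needed.

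**The size.** It rests wholly on assumed variances, and at zero school-by-time variance there is no inflation. This stands. The definition of τ² also matters. If the same percentages are read as the variance of a random time slope by school, then VIF = 1 + mτ²/(2σ²). Type I error becomes 8.6%, 12.1% and 18.6% at m = 60, and 11%, 17% and 26% at m = 100.

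**The ninth-grade comparison.** Its clusters are smaller. With an assumed 25 pairs per school (equal grades), VIF is 1.25, 1.5 and 2.0, and the error is 8%, 11% and 17%. With 15 pairs (60% of 25), it is 6.8%, 8.6% and 12.1%.

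**Scope of the check.** Exact cancellation holds for linear models with complete pairs. A simulation with 100 pre-surveys and 60 post-surveys per school, treating variance components as known, still gave 13%, 21% and 30%, and 4.4% at zero variance. The logistic models were not simulated, but they omit the same term.

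**Importance.** The sample size is feasibility-based, the randomised contrast is secondary, and no bias in the point estimates is shown. All true, but the plan promises p-values and intervals, and its primary parameter is affected.

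These points qualify the size of the problem. They do not remove it.

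**Conclusion.** The concern holds. As specified, the models give inference about change as if students within a school changed independently, in a trial that randomises and implements by school. This affects the primary time parameter in each arm and the only randomised contrast.

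Under the Section 8.3 model with random intercepts, and the variances assumed above, a nominal 5% test has a real error of roughly 12% to 29% at 60 pairs per school and 17% to 38% at 100. It is lower for ninth graders alone or if the percentages describe slope variance, and 5% if schools do not differ in change at all. The document does not claim that they do not, and 10 schools could not establish it.

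Section 1.1 mentions six schools per arm, against five elsewhere. Six would make the degrees of freedom 5 and 10 and would not alter the conclusion.

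**What to change.** In Section 8.3, add a random school-by-time effect (a random time slope by school) to every model, primary and secondary, and name the degrees-of-freedom method, Kenward-Roger or Satterthwaite. With complete pairs and equal school sizes, the equivalent is a t test on school-mean changes: 4 df within arm and 8 df between arms. State in advance that the school-level version is used for binary items and whenever the school-by-time variance is estimated at zero. Settle the number of schools per arm so that the degrees of freedom are fixed.

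The cost is a line or two of specification and no new data. The intervals will be wider for two reasons: the critical value rises from 1.96 to 2.78 (4 df) or 2.31 (8 df), and the standard error grows by √VIF. At VIF = 2.2, for example, they are √2.2 × 2.78/1.96 ≈ 2.1 times as wide within arm and √2.2 × 2.31/1.96 ≈ 1.75 times between arms. That is the precision that five schools per arm can support under that assumption.

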#### School Staff Semi-structured Interviews

Interviews will be analyzed to determine themes and Aavidum curriculum/club impact (Aim 3). Guided by [name] qualitative analysis expertise, thematic categories will be developed by reading and coding themes from the interview transcripts. Themes will be compared and contrasted to illustrate impacts of Aavidum on the selected high schools.

## 9.0 Data and Safety Monitoring Plan

**This section is required when research involves more than Minimal Risk to subjects as defined in “HRP-001 SOP- Definitions.”**

Minimal Risk is defined as the probability and magnitude of harm or discomfort anticipated in the research that are not greater in and of themselves than those ordinarily encountered in daily life or during the performance of routine physical or psychological examinations or tests. For research involving prisoners, Minimal Risk is the probability and magnitude of physical or psychological harm that is normally encountered in the daily lives, or in the routine medical, dental, or psychological examination of healthy persons.

**Please complete the sections below if the research involves more than minimal risk to subjects, otherwise indicate each section as not applicable.**

[Do not type here]

### 9.1 Periodic evaluation of data

Describe the plan to periodically evaluate the data collected regarding both harms and benefits to determine whether subjects remain safe.

Not applicable: This study does not involve more than minimal risk to subjects, and the magnitude of harm/discomfort is not greater than that ordinarily encountered in daily life.

### 9.2 Data that are reviewed

Describe the data that are reviewed, including safety data, untoward events, and efficacy data.

NA

### 9.3 Method of collection of safety information

Describe the method by which the safety information will be collected (e.g., with case report forms, at study visits, by telephone calls and with subjects).

NA

**9.4 Frequency of data collection**

Describe the frequency of data collection, including when safety data collection starts.

NA

**9.5 Individuals reviewing the data**

Identify the individuals who will review the data. The plan might include establishing a data and safety monitoring committee and a plan for reporting data monitoring committee findings to the IRB and the sponsor.

NA

**9.6 Frequency of review of cumulative data**

Describe the frequency or periodicity of review of cumulative data.

NA

**9.7 Statistical tests**

Describe the statistical tests for analyzing the safety data to determine whether harms are occurring.

NA

**9.8 Suspension of research**

Describe any conditions that trigger an immediate suspension of research.

NA

**10.0 Risks**

List the reasonably foreseeable risks, discomforts, hazards, or inconveniences to the subjects related to the subjects' participation in the research. Include as may be useful for the IRB's consideration, a description of the probability, magnitude, duration and reversibility of the risks. Consider all types of risk including physical, psychological, social, legal, and economic risks. Note: Loss of confidentiality is a potential risk when conducting human subject research.

- If applicable, indicate which procedures may have risks to the subjects that are currently unforeseeable.
- If applicable, indicate which procedures may have risks to an embryo or fetus should the subject be or become pregnant.
- If applicable, describe risks to others who are not subjects.

Risks involved in participating in this study are low. The questions asked in the surveys and interview are not sensitive in nature. Loss of confidentiality is a potential risk.

## 11.0 Potential Benefits to Subjects and Others

### 11.1 Potential Benefits to Subjects

Describe the potential benefits that individual subjects may experience from taking part in the research. If there is no direct benefit to subjects, indicate as such. Compensation is not considered a benefit. Compensation should be addressed in section 13.0.

Potential benefits to individual 9th grade students who receive the Aevidum curriculum include increased knowledge about mental health and help-seeking behaviors.

### 11.2 Potential Benefits to Others

Include benefits to society or others.

There is a potential benefit for the school to improve referrals for student mental health as well as the climate within the school building. Additionally, a potential benefit exists for the Aevidum initiative to establish an evidence-base.

## 12.0 Sharing Results with Subjects

Describe whether results (study results or individual subject results, such as results of investigational diagnostic tests, genetic tests, or incidental findings) will be shared with subjects or others (e.g., the subject's primary care physicians) and if so, describe how information will be shared.

Study results will not be shared with individual students who complete the pre-post surveys (University of Michigan Depression Center (UMDC) Peer-to-Peer Depression Awareness Assessment) or with faculty/school staff members who participate in the semi-structured Zoom interviews.

## 13.0 Subject Payment and/or Travel Reimbursements

Describe the amount, type (cash, check, gift card, other) and timing of any subject payment or travel reimbursement. If there is **no** subject payment or travel reimbursement, indicate as not applicable.

**Extra or Course Credit:** Describe the amount of credit **and** the available alternatives. Alternatives should be equal in time and effort to the amount of course or extra credit offered. It is not acceptable to indicate that the amount of credit is to be determined or at the discretion of the instructor of the course.

**Approved Subject Pool:** Indicate which approved subject pool will be used; include in response below that course credit will be given and alternatives will be offered as per the approved subject pool procedures.

### Schools

The 5 of the 10 schools that are randomly assigned to implement 2 Aevidum club activities will receive a \$1,000 stipend to support club activities during the 21-22 academic school year. The remaining 5 schools who are randomly assigned to implement just the Aevidum curriculum will receive a \$1,000 stipend for club activities at the end of the 2021-2022 school year after completion of the research.

An incentive will be offered to schools who have post-survey completion rates of 60%. Schools who hit this goal will be sent an additional \$100 stipend to put towards their Aevidum club.

### Student Pre- and Post- Survey

All students who complete the pre and post surveys (University of Michigan Depression Center (UMDC) Peer-to-Peer Depression Awareness Assessment) will have the chance to be entered into a drawing to receive an Amazon electronic gift card. Among these, eight students (four after pre-test and four after post-test) from each of the 10 participating high schools (total 96 students) will be chosen as winners. After completion of the pre-survey, four students will be randomly chosen to win a \$20 gift card from each school. After completion of the post-survey, four students will be randomly chosen to win a \$30 gift card from each school. Participants will receive the gift card via email within 2 weeks of closing either the pre or post survey respectively.

#### School Staff Semi-structured Interviews

Faculty advisors/school staff who participate in the semi-structured interviews will be compensated with a \$25 electronic gift card for their time. Participants will receive the electronic gift card via email within 2 weeks of participating in the interview.

#### School Staff Educator Training Feedback Survey

School staff who participated in the educator training at the beginning of the school year will have their provided email address entered into a raffle for the chance to win a \$10 Amazon electronic gift card. 10 winners will be selected and they will receive the gift card via email within 3 weeks of completing the survey.

### **14.0 Economic Burden to Subjects**

#### **14.1 Costs**

Describe any costs that subjects may be responsible for because of participation in the research.

There are no financial costs associated with participating in this research.

#### **14.2 Compensation for research-related injury**

**If the research involves more than Minimal Risk to subjects, describe the available compensation in the event of research related injury.**

**If there is no sponsor agreement that addresses compensation for medical care for research subjects with a research-related injury, include the following text as written - DO NOT ALTER OR DELETE:**  
It is the policy of the institution to provide neither financial compensation nor free medical treatment for research-related injury. In the event of injury resulting from this research, medical treatment is available but will be provided at the usual charge. Costs for the treatment of research-related injuries will be charged to subjects or their insurance carriers.

**For sponsored research studies with a research agreement with the sponsor that addresses compensation for medical care for research-related injuries, include the following text as written - DO NOT ALTER OR DELETE:**

It is the policy of the institution to provide neither financial compensation nor free medical treatment for research-related injury. In the event of injury resulting from this research, medical treatment is available but will be provided at the usual charge. Such charges may be paid by the study sponsor as outlined in the research agreement and explained in the consent form.

N/A

